## Appendix A

Assessment of Acute Toxicity Form to be completed by Surgical Team immediately after resection and at the Post Op Visit.

Field	Result
To be Recorded in the Operative Note	
Operating Time (min)	
Estimated Blood Loss (ml)	
Surgeon's Assessment of Fibrosis (Expected, Increased, Markedly Increased)	
To be Recorded at the Post Op Visit	Date of Visit:
Length of Hospitalization post-surgery including any re-admissions (days). Described any re-admissions	
Anastomotic Leak (yes/no) If so described	
Post-Surgery Infection Requiring Antibiotics (yes/no) If so described	
Wound healing complications that are worse than usual? (yes/no) If so described	

Name of person completing the form:

Date form completed:

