Building upon this experience, a prospective study of 15 patients from Harvard demonstrated that neoadjuvant short course RT using 25 Gy in 5 fractions to the pancreatic bed and regional lymph nodes using proton therapy and concurrent capecitabine was feasible and well tolerated. Acute grade 3 toxicity was noted in 4 of 15 patients. 11 of 15 patients underwent surgical resection but no patients experienced delays or exclusion from surgery due to toxicity from neoadjuvant treatment. Evaluation of 30 day post-operative results showed no deaths or anastomotic leaks. 9 of 11 patients who underwent surgery had R0 resections and 10 of these patients were able to receive post-operative gemcitabine. After a median follow up of 12 months, one year overall survival was 75% for the entire group. Of 11 surgical resected patients, 10 are still alive at last follow up. Of 15 patients treated with neoadjuvant therapy, only 1 patient with a positive surgical margin experienced local progression. No patient experienced nodal or regional failure but 8 patients developed metastatic disease.

A similar study was repeated, also at Harvard, using photon (conventional x-rays) instead of proton radiation therapy. However, compared with the proton study a higher rate of fibrosis (63% vs. 27%) was noted during surgery leading to a mean increase in operative time of 69

minutes. Dosimetric comparisons revealed that patients undergoing photon irradiation had significantly increased low dose radiation exposure to the abdominal organs. Due to this complication, the study was terminated after accrual of 10 of 12 planned patients.

While the Harvard study with neoadjuvant proton therapy achieved excellent results, protons are not widely available at most centers including ours. Therefore, we believe that there is a need for continued investigation of neoadjuvant photon radiation therapy for pancreatic cancer. We hypothesize that delivering high dose photon radiation to the gross disease using stereotactic localization (SBRT) without elective nodal irradiation can effectively reduce local recurrence while minimizing the fibrosis noted in the Harvard Photon study.

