We are not aware of any prospective reports of using SBRT alone as neoadjuvant treatment for resectable pancreatic cancer. However, there are several single institution experiences which show that SBRT can be safely delivered for locally advanced pancreatic cancer (LAPC). Choung et al. reported treating LAPC with induction chemotherapy followed by 5 fraction SBRT. Dose painting technique of 7-10 Gy/ Fraction to the region of vessel abutment and 5-6 Gy/fraction to the remainder of the tumor was utilized. Of 73 patients evaluated, no patients developed grade 3 or higher acute toxicity and only 5% developed grade 3 or higher late toxicity.

Since SBRT requires large doses of radiation to be accurately delivered, Chuong et al and many other authors have utilized fiducial placement in the tumor for more precise radiotherapy targeting. Although biliary stents have sometimes been used as a surrogate for tumor location, a study of 11 patients demonstrated that biliary stents are not reliable enough to substitute for fiducials in SBRT targeting. Fiducial placement using endoscopic ultrasound (EUS) has been demonstrated to be both feasible and safe.

Based on data from the aforementioned studies, we believe that our protocol which uses photon irradiation of 25 Gy in 5 fractions to the gross disease alone using fiducial localization and stereotactic guidance without chemotherapy will be able to achieve a favorable therapeutic ratio. The rationale is to deliver a dose of radiation that will sterilize microscopic disease at the margins thus decreasing the risk of local recurrence. By targeting the gross disease alone, we hope to minimize the volume of tissue treated and avoid the increase in fibrosis noted in the Harvard photon study. Using radiation therapy alone without chemotherapy will decrease the duration and toxicity of neoadjuvant therapy thereby allowing patients to proceed quickly to definitive surgical resection. After, resection, full dose chemotherapy can then be delivered without interruption with the aim of reducing distant metastatic disease.

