### **2.2 Primary Objectives**

- a) To evaluate the feasibility and tolerability of short course preoperative stereotactic body radiation therapy for resectable pancreas cancer
- b) To determine the rate of Grade 2 or greater acute toxicity of neoadjuvant stereotactic body radiation therapy
- c) To determine intraoperative and postoperative surgical morbidity following neoadjuvant treatment including the amount of fibrosis and total operative time.

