## 6.3 Documentation of Adverse Events

All adverse events, whether observed by the Investigator, elicited from or volunteered by the subject, will be documented. Each adverse event will include a brief description of the experience, the date of onset, the date of resolution, the duration and type of experience, the severity, and the relationship to SBRT, contributing factors, and any action taken with respect to the planned radiation therapy. In addition, any toxicity leading to radiation treatment break and delay in surgical resection beyond 3 weeks post SBRT will be noted.

All patients are expected to undergo surgical resection within 3 weeks after radiation therapy. Any Intraoperative complications including blood loss, total operative time and amount of fibrosis noted by the surgeon will be recorded in the operative report. Post-operative complications including delayed wound healing, blood loss, infection, length of hospital stay, incidence of pancreatic leak, hospital readmissions for complications will also be recorded. Appendix A lists the data the surgical oncology team is responsible for recording.

Treatment related late complications including but not limited to duodenal and intestinal ulceration, perforation, gastritis, bowel adhesions and obstruction, will be recorded at follow ups up to 5 years after treatment.

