## 7. RISK/BENEFIT ASSESSMENT

This study is being conducted because the investigators believe that treating pancreatic adenocarcinoma with preoperative SBRT may improve outcome compared with more conventional treatment. There have been several small-scale studies at other institutions (as documented in the introduction) which have shown delivering SBRT to the pancreas can be safe and effective. However, this technique has not been attempted at URMC. We aim to study whether neoadjuvant SBRT is feasible at URMC. There are benefits and risks associated with this study as documented below. The investigators believe that the benefits outweigh the potential risks for patients enrolled on this study.

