Investigators will conduct continuous review of data and patient safety. The Investigator will submit quarterly progress reports of these data to the Clinical Trials Monitoring Committee for review [Appendix C]. The review will include for each treatment arm/dose level: the number of patients enrolled, withdrawals, significant toxicities as described in the protocol, serious adverse events both expected and unexpected, dose adjustments, and responses observed. The PI maintains a database of all adverse events with toxicity grade and information regarding treatment required, complications, or sequelae. The Investigator will submit a copy of the AE spreadsheet along with the Progress Report to the Clinical Trials Monitoring Committee for review. Actual review dates will be assigned when the 1st patient is accrued.

- Any serious adverse event that is serious, related AND unexpected must be reported within 10 calendar days to both the Safety Coordinator and the RSRB (see RSRB guidelines). The DSMC Chair will determine whether further action is required, and when patient safety is of concern, an interim meeting may be called.
- Serious adverse events that are related AND expected or unrelated AND unexpected will be reported to the Committee for review at the quarterly meeting. SAE reports are expected to include sufficient detail so that the DSMC can determine the severity, toxicity grade, expectedness, treatment required, and a follow up report documenting resolution or if there are sequelae. Unless otherwise specified in the protocol, serious adverse events that require detailed reports (but not necessarily expedited) are expected, related, non-hematologic toxicities of grades 3, 4 or 5.

We plan to publish a descriptive analysis of the results including acute and late toxicity including surgical morbidity. We plan to report oncologic outcomes including median overall survival, progression free survival, local progression free survival and distant progression free survival. Analysis will be using Kaplan-Meier method. Survival time will be measured from the date of diagnosis. A local recurrence will be defined as any evidence of tumor recurrence within the PTV. Whether local recurrence occurred in conjunction with, before or after distant recurrence will be noted.

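### Does the Appendix A fibrosis rating need a stated reference for its lowest level?

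*Combined protocol and SAP*

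**What the plan says.** Primary objective (c) in Section 2.2 covers "intraoperative and postoperative surgical morbidity following neoadjuvant treatment including the amount of fibrosis" together with total operative time. Section 6.3 has the surgeon's note on fibrosis placed in the operative report and adds that "Appendix A lists the data the surgical oncology team is responsible for recording". In Appendix A the item reads "Surgeon's Assessment of Fibrosis (Expected, Increased, Markedly Increased"; it sits in the operative-note block with operating time and estimated blood loss.

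Section 1 explains the interest in fibrosis. In the earlier photon study, compared with the proton study, "a higher rate of fibrosis (63% vs. 27%) was noted during surgery", mean operative time rose by 69 minutes, and because of this complication "the study was terminated after accrual of 10 of 12 planned patients". The present trial treats gross disease alone in the hope that it will "avoid the increase in fibrosis noted in the Harvard photon study".

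Section 9 plans a descriptive report that includes surgical morbidity, with 18 patients enrolled and 12 evaluable.

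**The concern.** The trial has a single arm, so no unirradiated patient in the series shows the surgeon what the lowest level should look like. The rating is made by someone who knows that SBRT was given, on a form headed as an acute toxicity assessment. Two readings are open: no more fibrosis than in an ordinary Whipple, or no more than one expects after radiation. Under the second, fibrosis caused by SBRT would be recorded at the lowest level, which is the level that favours the trial's hypothesis. Two surgeons could also use different references within one small series. Because the rating is made at operation, it cannot be repeated reliably afterwards. At stake would be the descriptive result for a component of a primary objective that bears directly on the rationale.

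**Working it through.** **Is a reference given anywhere?** Fibrosis is mentioned in Section 1, Section 2.2, Section 6.3 and Appendix A. None of these states a comparator for the lowest level. Bowel adhesions (Section 6.3) and scar tissue (Section 7.2) appear only as late effects and do not supply one. The omission is confirmed.

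**Which reading does the text support?**

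- *Ordinary Whipple.* The levels above the lowest are *Increased* and *Markedly Increased*, which presuppose a norm that is exceeded. The wound-healing item on the same form asks about complications worse than usual. Section 7 says that "this technique has not been attempted at URMC", so local surgeons have no post-SBRT norm to rate against. The form's title points the same way, since a toxicity form exists to flag what the treatment caused.
- *Expected after radiation.* In favour are the universal exposure and the word *Expected* itself, where the wound-healing item speaks of what is usual. Section 9 uses a similar word in "Serious adverse events that are related AND expected or unrelated AND unexpected will be reported to the Committee for review", but that sentence classifies serious adverse events for the monitoring committee and has no link to an operative-note field.

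The first reading is clearly the stronger.

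**What depends on the rating?** Section 9 gives no alpha, power or target rate. Its stopping provisions turn on grade 3 or greater toxicity attributable to SBRT and on loss of eligibility for resection; neither refers to this item. The plan states no figure that can be reproduced from the rating, and none changes with the reference chosen.

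**How far could it move the report?** Inputs: 12 evaluable patients (Section 9) and the two earlier rates, 27% and 63% (Section 1). Assumptions: all 12 are rated, and the upper two levels count as fibrosis. The protocol does not make that link.

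- One rating: 1/12 = 8.3 percentage points.
- Patients corresponding to each earlier rate: 12 × 0.27 = 3.24 and 12 × 0.63 = 7.56. The difference is 7.56 − 3.24 = 4.32, about four patients.
- Exact (Clopper-Pearson) 95% limits, with lower limit the 0.025 quantile of Beta(x, n − x + 1) and upper limit the 0.975 quantile of Beta(x + 1, n − x): for 3/12, 5.5% to 57.2%; for 8/12, 34.9% to 90.1%.

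A shift of four patients would therefore change the description, but it needs about a third of the ratings to be made against the less natural reference. The two earlier rates are weak benchmarks in any case: the photon study accrued 10 patients and 11 were resected in the proton study.

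**Is there a cross-check?** Operating time and blood loss are numeric and come from the same form, and operative time is the quantity through which Section 1 describes the earlier harm. The operative report can be re-read if it describes the fibrosis. Section 5.2.1 asks pathology to note treatment effects. None of these replaces the rating, but together they are a partial check on it.

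**The case for a change.** The strongest case for a change is that fibrosis drives the design, that the only direct measure of it has no stated anchor, and that any misreading errs in favour of the hypothesis. Naming the reference would cost one line on the form and need no new data. A later reader cannot verify from the protocol which reference the surgeons used.

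The omission stands, as do the direction of the possible error and the low cost. What does not stand is the step from omission to defect. The text already leans to one reading, and nothing shows that a surgeon at this single centre would take the other. The claim that an error could never be recovered is too strong, given the other operative data. A stated anchor would also leave the rating subjective and unblinded. One detail needs care: not every patient need have had the full course before resection, because Section 6.5 allows SBRT to be stopped early. Exposure may be partial in some, which does not alter the reasoning.

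**Conclusion.** No change to the plan is needed. This is a missing definition that surgeons and analysts would fill sensibly, by rating against an ordinary pancreaticoduodenectomy and reporting the count at each level. The effect on any planned inference is nil, because none is planned on this item. The effect on the description is at most 8.3 points for each rating made against the other reference, with no evidence that any would be. The conclusion rests on two assumptions: that the surgical team takes the natural reading, and that fibrosis stays a descriptive outcome alongside operating time and blood loss. Confirming the reference with the surgeons would be a harmless courtesy, but the plan works without it.

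### Appendix A, the surgical form for primary objective (c), does not match section 6.3 on several post-operative items, and its fibrosis rating is not expressly required when a laparotomy ends without resection

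*Combined protocol and SAP*

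**What the plan says.** Section 2.2(c) makes surgical morbidity a primary objective: "To determine intraoperative and postoperative surgical morbidity following neoadjuvant treatment including the amount of fibrosis and total operative time".

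Section 6.3 says what is to be collected. For the operation: "Any Intraoperative complications including blood loss, total operative time and amount of fibrosis noted by the surgeon will be recorded in the operative report". For the period after it: "Post-operative complications including delayed wound healing, blood loss, infection, length of hospital stay, incidence of pancreatic leak, hospital readmissions for complications will also be recorded". It then names the instrument: "Appendix A lists the data the surgical oncology team is responsible for recording".

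Appendix A is to be completed straight after resection and again at the post-operative visit. Its operative block asks for operating time, estimated blood loss and a three-level fibrosis rating by the surgeon. Its post-operative block has four items:

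- hospital days, as "Length of Hospitalization post-surgery including any re-admissions (days", with a request to describe any readmission;
- anastomotic leak, yes/no with description;
- infection, yes/no with description, if antibiotics were required;
- wound healing, as "Wound healing complications that are worse than usual? (yes/no) If so described".

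Section 4.3.3 allows an attempted resection to be aborted when more advanced or metastatic disease is found. A patient whose resection cannot be completed because of advanced disease is withdrawn from the protocol. Section 9 plans a descriptive report that includes surgical morbidity, with no test or threshold attached to it.

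**The concern.** The form is the designated instrument for a primary objective, and in a single-arm study (section 2.1) the results can be read only against other series. That requires plain counts of events. A wound item already netted against the surgeon's idea of usual is not a plain count, and the threshold may differ between surgeons and from any published series. Section 7.2(b) itself lists delayed wound healing as a possible effect of radiation, so the filter falls on a risk that the protocol names. A stay figure with readmission days added in is neither an index length of stay nor a readmission measure.

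Fibrosis raises a separate question. Section 1 reports that the earlier photon study stopped early after more fibrosis than in the proton study (63% against 27%) and a mean increase of 69 minutes in operative time. Avoiding that is the stated rationale for this trial. If the fibrosis rating is collected only after completed resections, operations that end without one may be missing from the structured data.

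**Working it through.** No formula in the plan applies: the documents attach no sample size calculation, error rate or threshold to surgical morbidity. The check is an item-by-item comparison of 6.3 with Appendix A.

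| Item named in 6.3 | What Appendix A collects | Result |
|---|---|---|
| Intraoperative blood loss | Estimated volume in ml | Field present |
| Operative time | Minutes | Field present |
| Fibrosis | Three-level surgeon rating | Field present |
| Delayed wound healing | Yes/no, only if beyond what is usual | Filtered, threshold undefined |
| Infection | Yes/no, only if antibiotics were needed | Filtered |
| Length of stay | One total that includes readmission days | Merged |
| Readmission for complications | Free-text description; no yes/no, no day count, not limited to complications | Merged, unstructured |
| Pancreatic leak | Any anastomotic leak, yes/no with description | Different label, site not requested |
| Post-operative blood loss | Nothing; the only blood-loss field is in the operative block | No field |

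Tally: 3 intraoperative items with a field, 5 post-operative items filtered, merged or differently labelled, and 1 absent; 3 + 5 + 1 = 9.

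**Stay.** Take two invented patients. One has an 8-day index stay and a 6-day readmission; the other has an uncomplicated 14-day stay. The numeric field gives 8 + 6 = 14 for the first and 14 for the second. The description shows that the first was readmitted, but the index stay can be recovered (14 − 6 = 8) only if whoever completes the form happens to write down the 6 days.

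**Wound and infection filters.** The documents give no event rates, so the undercount is unknown. With the planned 12 evaluable patients (sections 3.1 and 9), screening out k events lowers the reported rate by k/12. Assumed range: k = 0 gives no change; k = 1 gives 1/12 = 8.3 percentage points; k = 2 gives 2/12 = 16.7; k = 3 gives 3/12 = 25.0.

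**Trigger.** The form's instruction refers to resection, while 4.3.3 foresees laparotomies that stop short of it. No sentence in 6.3, 4.3.3 or Appendix A expressly asks for the form after such an operation.

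**The case against.** The strongest reply is that the form is not the only source. Section 6.1 defines adverse events broadly, related to treatment or not, and grades them by CTCAE version 4.0. Section 6.3 requires all of them to be documented with dates and severity, 6.4 covers death and hospitalization, and section 9 describes a database of all adverse events with toxicity grade. Post-operative bleeding, or a wound problem of ordinary severity, should therefore be recorded somewhere. This largely stands, and it means that the absence of grades on the form is not in itself a loss. It does not repair the form, however. A wound event could be in the database while the form says no, and section 9 does not say which source feeds the published morbidity analysis.

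It can also be said that delayed healing is already a departure from the usual, so the filter may remove little. That is possible, and it is why no undercount is asserted. But asking whether complications exceed the usual is a different question from asking whether healing was delayed, and the difference is left undefined.

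A reader might go further than the documents allow:

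- *Pancreatic leak is omitted.* It is not. A leak at the pancreatic anastomosis scores yes and can be described; only the site is not requested. Section 1 also uses the pooled term for the proton study, so the pooled item is worth keeping.
- *Intraoperative complications are omitted.* All three items that 6.3 names have fields. What is missing is an open field for others, which 6.3 sends to the operative report.
- *Stay and readmission can never be separated.* The free text may allow it.
- *An abandoned operation leaves no record.* An operative report would exist, and section 9 closes accrual if SBRT toxicity alone makes a patient ineligible for resection. The only reason for aborting that 4.3.3 describes is advanced or metastatic disease; abandonment for fibrosis is a hypothetical case. The gap is that the structured rating is not expressly required.

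**Conclusion.** The mismatch is real and limited. Five of the six post-operative items in 6.3 reach the form filtered, merged or under another label, and the sixth, blood loss, has no field. The form's fibrosis rating is not expressly required after a laparotomy without resection.

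It would be wrong to conclude that primary objective (c) goes unmeasured. Fibrosis and operative time, the two items that the objective names, are captured for resected patients, as is operative blood loss, and adverse event documentation gives partial backup. The weakness is in the comparability and consistency of the post-operative data; lost data are not demonstrated. The conclusion assumes that the surgical team completes the form as worded and that the published morbidity figures draw on it. It needs no assumption about how often the filtered events occur.

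**What to change.** Revise Appendix A to match 6.3:

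- Record any wound complication (yes/no, description, CTCAE version 4.0 grade) and drop the comparison with the usual.
- Record any post-operative infection, and note separately whether antibiotics were needed.
- Record index length of stay in days, and readmission as its own item (yes/no, reason, days).
- Keep the anastomotic leak item and add the site (pancreatic or other).
- Add a field for post-operative bleeding.
- Complete the operative block after every laparotomy, with a line for whether resection was completed and, if not, why.

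This is a short revision of a one-page form and changes no treatment. It is best made before enrollment, because a judgment of what was usual is hard to reconstruct later. The downside is a slightly longer form and possibly higher reported morbidity counts.
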